10.5.4 Time to Return to Usual Health

Definitions:

Return to Usual Health “Yes” response to the daily FLU-PRO global assessment question, “Have you returned to your usual health today?” maintained for at least two consecutive daily diary periods without symptom relief medication during or between those two daily diary periods

Time of Return to Usual Health The time of the first diary entry in which the subject achieves Return to Usual Health

Time to Return to Usual Health Time (hours) from first dose to the Time of Return to Usual Health

Variables Used for the Analysis

The analysis will require the following variables:

Variable	Source	Format/Notes
Date and time of first medication intake	CRF	
Date and time of completion for each symptom assessment record	Subject diary	
Return to usual health global assessment question response	Subject diary	The return to usual health question will have possible response values of “Yes” or “No”. In the event that the response was not recorded at a specified time point (e.g., Day 2), the missing data will not be imputed.
Date and time of symptom relief medication intake	Sponsor-provided listing	The list of symptom relief medications will be selected from the listing of all concomitant medications prior to unblinding.

Analysis

The efficacy parameter, Time to Return to Usual Health, will be derived as follows:

Event: Time of Return to Usual Health – time of the first dose

Censored: Time of last ability assessment – time of the first dose

If Return to Usual Health is achieved at the time of the first symptom assessment diary record, the subject will be excluded from the analysis.

If the subject does not achieve Return to Usual Health prior to the subject’s last available diary assessment, but records a “Yes” for the return to usual health global assessment question at the last available diary assessment with no evidence of symptom relief medication intake during that diary period, time of Return to Usual Health will be considered to have occurred at the time of the last available diary assessment.

Time to Return to Usual Health for the NTZ treatment group will be compared to that of the placebo treatment group using a Gehan-Wilcoxon test stratified for (1) onset of illness to time of first dose of study medication (0-24, >24-≤36, or >36 hours from onset), and (2) whether the vaccination status (Y/N). The comparison will be graphically depicted using Kaplan-Meier curves.

Analysis Population(s):	Confirmed Influenza
Derived Variables:	Event: Time of Ability to Perform All Normal Activities – time of the first dose Censored: Time of last ability assessment – time of the first dose

10.5.5 Change in Influenza Virus Titer (TCID₅₀) from Baseline to Day 2 and from Baseline to Day 3

Variables Used for the Analysis

The analysis will require the following variables:

Variable	Source	Format/Notes
TCID ₅₀ virus titer	Laboratory data	TCID ₅₀ values will be reported as “10 ^{-3.2} ”, for example. For analysis purposes, the values should be negative log-transformed. For the example above, the analysis value would be “3.2”.

Analysis

Mean changes in influenza viral titers from baseline to day 2 and from baseline to day 3 for the NTZ and the placebo treatment groups will be compared using a t-test.

Analysis Population(s):	Confirmed Influenza
Derived Variables:	Mean change in influenza viral titer from baseline to day 2: mean of (day 2 TCID ₅₀ value – baseline TCID ₅₀ value) for each subject within the treatment groups Mean change in influenza viral titer from baseline to day 3: mean of (day 3 TCID ₅₀ value – baseline TCID ₅₀ value) for each subject within the treatment groups

10.5.6 Proportions of Subjects with Detectable Virus at Days 2, 3 and 7

Variables Used for the Analysis

The analysis will require the following variables:

Variable	Source	Format/Notes
TCID ₅₀ virus titer	Laboratory data	TCID ₅₀ values will be reported as “10 ^{-3.2} ”, for example. For analysis purposes, any numerical result will be treated as “positive”. A result of “No Virus Isolated” will be treated as “negative”.

Analysis

The proportion of subjects with a positive result by TCID₅₀ at each of days 2, 3, and 7 will be compared across treatment groups using a Fisher’s exact test.

Analysis Population(s):	Confirmed Influenza
Derived Variables:	Proportion of subjects with detectable virus at day 2: Number of subjects with “positive” result by TCID ₅₀ at day 2 divided by the total number of confirmed influenza subjects with a day 2 TCID ₅₀ result for each treatment group Proportion of subjects with detectable virus at day 3: Number of subjects with “positive” result by TCID ₅₀ at day 3 divided by the total number of confirmed influenza subjects with a day 3 TCID ₅₀ result for each treatment group Proportion of subjects with detectable virus at day 7: Number of subjects with “positive” result by TCID ₅₀ at day 7 divided by the total number of confirmed influenza subjects for each treatment group (subjects with no TCID ₅₀ result at day 7 will be assumed to have a result of “negative” because day 7 samples were not tested by TCID ₅₀ if traditional viral culture was negative for the sample)

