- *Choice of Endpoints.* The primary efficacy endpoint for this study will be Time to Symptom Response based upon the FLU-PRO[®] instrument. This is directed to the way the patient “feels” as measured by his/her symptoms. A Symptom Response definition will be developed based upon a blinded review of FLU-PRO symptom scores (pooled for all subjects without regard to treatment group assignment so as to maintain blinding) and correlation of those scores to the time at which subjects report that they have returned to their usual state of health (a “yes” or “no” question incorporated into the daily Questionnaire). The Time to Symptom Response used for evaluating the primary endpoint will be calculated based upon this response definition and programmed prior to database unblinding for the primary analysis. This anchor-based approach to defining responders ensures that the symptom response definition is valid and meaningful for the subjects participating in each given clinical trial – a point that may be particularly important in the case of an illness like influenza that is not uniform from year to year.

The key secondary endpoint will be Time to Ability to Perform All Normal Activities. This endpoint will provide important information with respect to the way a patient “functions.” Each of the previous clinical trials of NTZ in subjects with influenza have indicated improvement in this endpoint while data collection from those studies has typically not extended out long enough to fully characterize the benefit.

Another secondary endpoint will be proportions of subjects experiencing complications of influenza. We do not expect to see enough complications of influenza in this population to demonstrate differences between treatment groups, and therefore, this endpoint is lesser in priority compared to Time to Ability to Perform All Normal Activities. All other efficacy endpoints will be considered exploratory.

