Time of FLU-PRO Domain Response:

For each domain, the start of the first daily diary period in which the FLU-PRO Domain Response is achieved and is maintained for at least 2 daily diary periods without symptom relief medication during those 2 daily diary periods

Time to FLU-PRO Domain Response:

Time (hours) from first dose to FLU-PRO Domain Response for each domain

Resolution of Acute Febrile Illness:

Oral temperature is recorded by the patient as $<100.4^{\circ}\text{F}$ ($<38^{\circ}\text{C}$) and symptom scores for each of “body aches or pains”, “chills or shivering”, “felt cold”, “felt hot” and “sweating” are 0 or 1 and remain so throughout 2 daily diary periods without symptom relief medication during those 2 daily diary periods

Time to Resolution of Acute Febrile Illness:

Time (hours) from first dose to resolution of acute febrile illness.

Return to Usual Health:

“Yes” response to the daily FLU-PRO global assessment question, “Have you returned to your usual health today?” maintained for at least 2 daily diary periods without symptom relief medication during those 2 daily diary periods

Time of Return to Usual Health:

The time of the first daily diary entry in which Usual Health is achieved and is maintained for at least 2 daily diary periods without symptom relief medication during those 2 daily diary periods

Time to Return to Usual Health:

Time (hours) from first dose to Time of Return to Usual Health

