14.2.5.1	Evaluation of Modified Symptom Response Definition	Table	Confirmed Influenza
14.2.5.2	Analysis of Time to Modified Symptom Response	Table	Confirmed Influenza
14.2.5.3	Graphical Representation of Time to Modified Symptom Response	Figure	Confirmed Influenza
14.2.6.1.x	Analysis of Time to Individual Symptom Response	Table	Confirmed Influenza
14.2.6.2.x	Graphical Representation of Time to Individual Symptom Response	Figure	Confirmed Influenza
14.2.7.1.x	Analysis of Time to FLU-PRO Domain Response	Table	Confirmed Influenza
14.2.7.2.x	Graphical Representation of Time to FLU-PRO Domain Response	Figure	Confirmed Influenza
14.2.8.1	Analysis of Time to Resolution of Acute Febrile Illness	Table	Confirmed Influenza
14.2.8.2	Graphical Representation of Time to Resolution of Acute Febrile Illness	Figure	Confirmed Influenza
14.2.9.1	Analysis of Time to Return to Usual Health	Table	Confirmed Influenza
14.2.9.2	Graphical Representation of Time to Return to Usual Health	Figure	Confirmed Influenza
14.2.10	Analysis of Changes in Influenza Virus Titer (TCID ₅₀)	Table	Confirmed Influenza
14.2.11	Proportions of Subjects with Detectable Influenza Virus on Days 2, 3, and 7	Table	Confirmed Influenza
14.2.12.1	Analysis of Mean Changes in Influenza Antibody Titers from Baseline	Table	Confirmed Influenza
14.2.12.2	Analysis of Proportions of Subjects with Seroprotected and Seroconverted Antibody Response	Table	Confirmed Influenza
14.2.13	Analysis of Plasma Tizoxanide and Tizoxanide Glucuronide Concentrations	Table	Confirmed Influenza
Safety Displays			
14.3.1.1	Summary of All Treatment Emergent Adverse Events	Table	All Treated
14.3.1.2	Number and Percent of Subjects with Treatment Emergent Adverse Events by System Organ Class and Preferred Term	Table	All Treated
14.3.1.3	Number and Percent of Subjects with Treatment Emergent Adverse Events by System Organ Class, Preferred Term and Severity	Table	All Treated
14.3.1.4	Number and Percent of Subjects with Grade ≥ 3 Treatment Emergent Adverse Events by System Organ Class and Preferred Term	Table	All Treated
14.3.1.5	Number and Percent of Subjects with Treatment Emergent Adverse Events by System Organ Class, Preferred Term and Relationship to Study Medication	Table	All Treated
14.3.1.6	Number and Percent of Subjects with Treatment Emergent Unexpected Adverse Events by System Organ Class and Preferred Term	Table	All Treated

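### In SAP 10.5.4 the Derived Variables row for Time to Return to Usual Health names the key secondary endpoint's event, and the section censors at the activity score in both places

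*SAP*

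**What the plan says.** SAP 10.5.4 defines the endpoint as "Time (hours) from first dose to the Time of Return to Usual Health". Return to usual health means a yes to the daily FLU-PRO global question on two consecutive diaries, without symptom relief medication. Protocol 8.3 gives the same endpoint: "Time (hours) from first dose to Time of Return to Usual Health".

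The Analysis text of SAP 10.5.4 then derives it as "Event: Time of Return to Usual Health – time of the first dose", with censoring given as "Censored: Time of last ability assessment – time of the first dose".

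The Derived Variables row that closes the section gives a different event: "Event: Time of Ability to Perform All Normal Activities – time of the first dose". Its censoring line is the same as in the Analysis text.

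SAP Appendix II plans Table 14.2.9.1, "Analysis of Time to Return to Usual Health", with Figure 14.2.9.2 and Listing 16.2.6.8 for the same endpoint. The endpoint's status is set in Protocol section 3, which names the primary and secondary endpoints and then states: "All other efficacy endpoints will be considered exploratory".

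**The concern.** One section gives two derivation rules for one variable, and the rules use different instruments. Usual health is a yes/no question within FLU-PRO. The activity endpoint is a score of 10 on a separate 0-10 scale. The SAP's Introduction says that the document details how variables are derived, so a row headed Derived Variables is a natural place for a programmer to look.

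A slip here could look plausible in the results. SAP 7.3 expects usual health to track ability to perform usual activities very closely, so an activity result under a usual-health title would not look odd on its own. Set beside the true activity result, it would make the two endpoints appear to agree perfectly, because one variable would be compared with itself.

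The censoring line is a second error. It appears in both places, so correcting only the event in the row would leave it standing.

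**Working it through.** No formula or sample-size figure is involved in the event error. The check is a comparison of the places that define or use the endpoint.

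| Place | Event | Censoring |
|---|---|---|
| Protocol 8.3 | Usual health | Not stated |
| SAP 10.5.4, definitions | Usual health | Not stated |
| SAP 10.5.4, Analysis text | Usual health | Last activity assessment |
| SAP 10.5.4, Derived Variables | Activity score of 10 | Last activity assessment |
| SAP 10.4.1, Derived Variables | Activity score of 10 | Last activity assessment |

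**Event.** Both lines of the 10.5.4 row equal the 10.4.1 row. The Derived Variables rows of 10.2.2, 10.4.3, 10.5.1, 10.5.2 and 10.5.3 each name their own endpoint, and only 10.5.4 names another section's. The outcome variable that 10.5.4 lists as required is "Return to usual health global assessment question response". No activity score is listed, so the row cannot be computed from the section's own inputs. This is a copying error and not a chosen analysis.

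**Consequence if the row is followed.** Sections 10.4.1 and 10.5.4 use the same population (Confirmed Influenza), the same stratified Gehan-Wilcoxon test and the same strata. Table 14.2.9.1 and Figure 14.2.9.2 would therefore duplicate Table 14.2.3.1 and Figure 14.2.3.2. The match could fall short of exact if the programmer took the event from the row but kept the 10.5.4 rules for first-diary exclusion and for a response at the last diary, since those rules refer to usual health.

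**Listing 16.2.6.8.** SAP Table 5 separately requires this listing to show the date and time of return to usual health beside the event and censored times. Event times taken from the row would not equal that date minus the first-dose date, except where a subject reached both endpoints at the same time.

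**Censoring.** The timing items that 10.5.4 requires are those of the symptom assessment records, not the activity assessments. Protocol 5.10 schedules FLU-PRO and the activity scale once daily, both between 7 pm and 11 pm.
- If both last answers come from the same evening and within the window, the two censoring times differ by at most 11 − 7 = 4 hours. Against the 504-hour follow-up in SAP 7.3 that is 4 / 504 = 0.8%.
- If the last answers are one day apart, the difference is 24 ± 4, that is 20 to 28 hours.
- Only subjects without an event are affected. The documents give no count of subjects whose last two answers fall on different days.

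**Reach.** SAP 10.2.1, step 1, builds the variable that marks return to usual health directly from the usual-health question, without using 10.5.4. The testing hierarchy in SAP 10.4 covers the primary endpoint, the activity endpoint and complications, and usual health is not in it.

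**The case against.** The strongest reply is that nobody reading the whole section could mistake the endpoint. The title, the definitions, the required variables, the Analysis event line, the last-diary rule and the test sentence of 10.5.4 all say usual health, and so does the protocol. A programmer would have to set all of that aside and import a variable that the section does not list. Two identical tables would also be easy to notice, and Listing 16.2.6.8 as specified in Table 5 would expose a mismatch. On this view the point is editorial.

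Much of this stands. The intended event is clear, and the harm depends on someone programming from the row. But the row is an operative derivation rule, and it is wrong as written. The reply also does not cover the censoring line, where the Analysis text and the row agree with each other and both name the wrong diary item.

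A reader might go further and infer one of the following. The documents support neither.
- *The primary endpoint is contaminated, because Symptom Response is anchored to usual health.* The anchor is defined separately in SAP 10.2.1, so the error in 10.5.4 does not reach it.
- *The error would create false independent support for the primary result.* Even a correct usual-health analysis would not be independent support, because the Symptom Response definition is chosen to minimise misclassification against that same question.

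**Conclusion.** The contradiction is real and can be verified from the text. The Derived Variables row of SAP 10.5.4 gives the key secondary endpoint's event, and both statements of the censoring rule in that section name the activity assessment.

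The effect is confined to one exploratory endpoint. Conditional on programming from the row, every event time behind Table 14.2.9.1 and Figure 14.2.9.2 would be that of the activity endpoint, and Listing 16.2.6.8 would be internally inconsistent. The documents do not show that the outputs will be programmed that way, so it would be too strong to say that the trial will report the wrong endpoint. The primary and key secondary analyses, alpha and power are untouched.

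With the event corrected but the censoring left as it is, the effect should be small. This rests on the two diary items normally being completed on the same evening, as Protocol 5.10 schedules them.

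**What to change.** Three lines in SAP 10.5.4:
- Derived Variables row, event: time of return to usual health minus time of first dose.
- Derived Variables row, censored: time of the last usual-health (FLU-PRO) assessment minus time of first dose.
- Analysis text, censored: the same wording as in the corrected row.

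The event line in the Analysis text is already right and stays. The change needs no new data and no change to the protocol, the test, the strata or the sample size. It can be made under the SAP's own provision for revision before database lock. If the outputs have already been programmed, check that Tables 14.2.9.1 and 14.2.3.1 are not the same result, and that the event times in Listing 16.2.6.8 agree with the usual-health dates beside them.

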the same time of day that the subject took his/her first dose of study medication (roughly 24 and 48 hours post-first dose). On day 3, the blood sample for pharmacokinetics will be collected before the dose. The nasopharyngeal swabs will be used to evaluate quantitative changes in viral shedding. The blood samples will be used to evaluate relationships between pharmacokinetics and virologic or clinical response. Study sites or subjects may opt out of the day 2 and day 3 visits due to site staffing, patient availability or other practical considerations or preferences; nevertheless, at least 75% of subjects enrolled in the trial are expected to complete the day 2 and day 3 visits and related procedures (for viral kinetics and pharmacokinetics).

A study physician, nurse or other site personnel will make daily telephone calls to subjects for the first five days of dosing to review symptoms and screen for influenza-related complications including sinusitis, otitis, bronchitis, pneumonia and central nervous system disease. Subjects will be referred for immediate care as needed based on the screening. [Note: In lieu of a telephone call, this information may be obtained during the day 2 or 3 office or home visits (see the preceding paragraph).] The study sites and subjects will be blinded from virology laboratory data until after study day 22 or, if earlier, until the subject is discontinued from the study. During the study period, each subject will be presumed to have influenza infection, and any worsening of symptoms or complications will be presumed to be influenza-related.

Subjects will return to the clinic on days 7 and 22 for post-treatment follow-up, including two nasopharyngeal swabs, drug accountability, reporting of adverse events and complications of influenza. Blood and urine samples for laboratory safety tests will be collected at day 7, and a blood sample for anti-influenza antibodies will be collected on day 22. A nurse or other study personnel will review the electronic patient diary entries daily (synchronized to a web-based data system) to ensure contemporaneous and complete recording of diary data. Subjects will maintain the electronic patient diaries until study day 22. Any visits that do not occur on the prescribed date, or within 1 day of that date in the case of the day 7 visit or within 3 days after that date in the case of the day 22 visit, will be recorded as protocol deviations.

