5.5 Day 2 and 3 Evaluations

A study physician, nurse or other study personnel will visit each subject at home (or at the clinic or another location as agreed with the subject) on each of days 2 and 3 to (i) collect two nasopharyngeal swabs for detecting (RT-PCR) and quantifying (TCID_{50}) influenza virus, and (ii) review symptoms and screen for influenza-related complications including sinusitis, otitis, bronchitis, pneumonia, central nervous system disease and worsening of pre-existing health conditions as well as adverse events. Subjects will be referred for immediate care as needed based on the screening. All information gained from these visits will be included in the case report forms for each subject. In addition, a blood sample for pharmacokinetics will be collected on day 3. The day 2 and day 3 visits will occur at approximately the same time of day that the patient took his/her first dose of study medication (approximately 24 and 48 hours after the first dose). On day 3, the blood sample for pharmacokinetics will be collected before the first dose of that day.

Study sites or subjects may opt out of these day 2 and day 3 visits due to site staffing, patient availability or other practical considerations or preferences; nevertheless at least 75% of subjects enrolled in the trial are expected to complete the day 2 and day 3 visits and related procedures (for viral kinetics and pharmacokinetics).

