5.9 Study Discontinuation

Rules for discontinuation of a patient or for discontinuing the study are provided in section 11.2. All subjects discontinued from the study before day 7 will be evaluated at study discontinuation using the procedures described above for day 7. All subjects discontinued from the study after day 7 will be evaluated at study discontinuation using the procedures described above for day 22.

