8 STATISTICAL CONSIDERATIONS

8.1 Sample Size Calculation

As described in section 7.3 below, the Symptom Response definition for this study will be derived from the subjects' FLU-PRO questionnaire responses. The FLU-PRO-derived endpoint is expected to track very closely to return to usual health status (a daily yes/no question in the FLU-PRO questionnaire). Patient-reported outcomes for time to return to usual health status have been shown to track very closely with time to ability to perform 100% of usual activities.^{27,28,29} We assume, therefore, that the cumulative distributions of time to Symptom Response for the placebo treatment group will closely reflect historical data (Romark studies RM08-3002 and RM08-3003 and oseltamivir studies WV15670 and WV15671) for time from first dose until the subjects report that they are able to perform 100% of usual activities. Based upon data from Romark studies RM08-3001, RM08-3002 and RM08-3003, we assume that treatment with NTZ should result in reduction of at least 40 hours in median time to symptom response with differences being less at the first

quartile and greater at the third quartile. Based upon this historical data, the following curves have been developed for determining sample size.

Based upon these curves, a sample size of 552 subjects with laboratory-confirmed influenza (i.e. 276 for each of the 2 groups) will provide 90% power to detect a statistically significant difference in the survival distributions between NTZ and placebo groups (2-sided alpha of 0.05). This calculation was performed for the Gehan rank test using SAS PROC POWER (SAS 9.4) with the curves shown above (proportion not recovering by the end of each day was used as input) and censoring at day 21 (hour 504). Assuming that 8% of subjects will have incomplete data, we arrive at a sample size of 600 subjects in total, 300 per treatment group to yield at least approximately 550 with complete data (all 600 subjects will be included in the primary analysis with subjects with incomplete data censored as of their last entry).

Based upon these calculations, the study will enroll at least 600 subjects with laboratory-confirmed influenza up to a maximum of 700 subjects with laboratory-confirmed influenza. We estimate that this will require enrollment of 800 to 1,200 subjects in total assuming a flu-positive rate between 50% and 75%.

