- The primary efficacy analysis will be repeated using only items from the four FLU-PRO domains (Body/Systemic, Throat, Chest/Respiratory and Nose) that correspond to the seven symptoms included in the traditional PRO instrument (feverishness, myalgia, headache, fatigue, sore throat, nasal obstruction and cough). For this secondary analysis, we will derive the Symptom Response definition in the same manner as for deriving the Symptom Response definition used in the primary analysis (after removing the Eye and Gastrointestinal symptoms).

Exploratory analyses will be performed as follows:

- For each of the 32 individual FLU-PRO symptoms, Time to Individual Symptom Response for the NTZ and placebo treatment groups will be compared using the Gehan-Wilcoxon test.
- For each of the 6 FLU-PRO domains, Time to FLU-PRO Domain Response for the NTZ and placebo treatment groups will be compared using the Gehan-Wilcoxon test.
- Time to Resolution of Acute Febrile Illness for the NTZ and placebo treatment groups will be compared using the Gehan-Wilcoxon test.
- Time to Return to Usual Health for the NTZ and placebo treatment groups will be compared using the Gehan-Wilcoxon test.
- Changes in influenza TCID₅₀ viral titers from baseline to day 2 and from baseline to day 3 for the NTZ and placebo treatment groups will be compared using a t-test.
- For subjects with laboratory-confirmed influenza, the proportions of subjects with influenza virus detected by culture in nasopharyngeal swabs collected at each of days 2, 3 and 7 will be compared for the two treatment groups using a Fisher's exact test.

Sensitivity analyses for the primary endpoint will include:

- Repeat the primary efficacy analysis, assigning a Time to Symptom Response of 21 days for subjects that discontinue prior to day 21 without achieving Symptom Response.
- Repeat the primary efficacy analysis for a “per protocol” subset.

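### SAP 10.5.6 scores confirmed-influenza subjects with no Day 7 swab as virus-negative, although its stated reason covers only collected swabs with a negative culture

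*SAP*

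**What the plan says.** SAP 10.5.6 compares the proportion TCID50-positive at Days 2, 3 and 7 with Fisher's exact test in the Confirmed Influenza population. At Days 2 and 3 the denominator is limited to subjects with a TCID50 result on that day. At Day 7 the positives are "divided by the total number of confirmed influenza subjects for each treatment group", with no result required. A subject with no TCID50 "result at day 7 will be assumed to have a result of" negative. The justification is that Day 7 samples were not titrated "if traditional viral culture was negative for the sample".

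The related provisions are:

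- **Population (SAP 8.1).** Membership of Confirmed Influenza rests on Baseline, Day 2 or Day 3 positivity. No Day 7 sample is needed.
- **Missing data (SAP 8.4, Table 3).** There is no virology entry.
- **Endpoint (Protocol 8.4.1).** The comparison is of "the proportions of subjects with influenza virus detected by culture in nasopharyngeal swabs collected at each of days 2, 3 and 7". Protocol 8.2, exploratory item vi, names culture and RT-PCR.
- **Early discontinuation (Protocol 5.9).** "All subjects discontinued from the study before day 7 will be evaluated at study discontinuation using the procedures described above for day 7".
- **Visit timing (Protocol 3).** "Any visits that do not occur on the prescribed date", outside the allowed windows, are recorded as protocol deviations.

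**The concern.** The rule is wider than its reason. The reason presupposes a sample that was collected, cultured and found negative. The rule has no such condition: it applies to anyone without a Day 7 TCID50 result, including a subject who missed the visit or was lost to follow-up.

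Such a subject stays in the denominator and can never enter the numerator. The reported proportion is then a minimum, shown in display 14.2.11 beside Day 2 and Day 3 rows that count only subjects with results. If swabs go missing more often in one arm, that arm looks virologically better for a reason unrelated to virus. SAP 10.5.6 does not ask for missing counts by arm, so a reader of that display could not see this.

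The results-only denominator at Days 2 and 3 is not at fault. Protocol 5.5 provides that "Study sites or subjects may opt out of these day 2 and day 3 visits", so gaps there are expected.

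**Working it through.** **No figure to reproduce.** The plan states no number for this rule. The only incomplete-data rate in the documents is in Protocol 8.1 ("Assuming that 8% of subjects will have incomplete data"), and it checks: 552 / (1 − 0.08) = 600. It describes incomplete data for the primary endpoint, not swabs, and is borrowed here only as an assumed average.

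**Does anything else remove subjects without a swab?**

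1. SAP 8.1 does not, because it ignores Day 7.
2. SAP 8.4 does not, because it has no virology rule.
3. Protocol 5.9 reduces the number by asking for Day 7 procedures at early discontinuation. It does not reach missed visits or loss to follow-up.

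The literal reading therefore stands.

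**Inputs.** 300 per arm (Protocol 8.1), 1:1 allocation, two-sided α = 0.05 (SAP 10.1). Assumed: true Day 7 positivity p = 10%, 20% or 30%; share without a swab m averaging 8%, split equally or as 5% v 11% or 4% v 12%; swabs missing independently of virus status.

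**Expected proportion.** Under the SAP rule it is p(1 − m).

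- Equal 8% missing, p = 20%: 0.20 × 0.92 = 18.4% in both arms, so no false gap. Fisher's test rejects 3.9% of the time under either rule.
- 4% v 12% missing, no true effect: the false gap is p × 0.08, that is 0.8, 1.6 and 2.4 points at p = 10%, 20% and 30%.

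**Rejection rate with no treatment effect** (exact enumeration of Fisher's test). SAP rule: 300 v 300 with event rates p(1 − m₁) v p(1 − m₂). Known-status denominator: 285 v 267 subjects (5% v 11% missing) or 288 v 264 (4% v 12%), with rate p in both arms.

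| p | Missing | SAP rule | Known status |
|---|---|---|---|
| 10% | 5% v 11% | 4.2% | 4.3% |
| 10% | 4% v 12% | 4.7% | 4.3% |
| 20% | 5% v 11% | 5.3% | 4.4% |
| 20% | 4% v 12% | 6.5% | 4.4% |
| 30% | 5% v 11% | 6.5% | 4.5% |
| 30% | 4% v 12% | 8.5% | 4.5% |

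The SAP-rule column lets the number of missing swabs vary; the other column fixes it. With counts fixed in both, the SAP rule gives 5.1% and 6.3% at p = 20%, and 6.2% and 8.1% at p = 30%. At p = 10% it stays below 5% either way.

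**If missingness depends on virus status.** Let positivity be 20% among swabbed subjects, m = 8%, and q the positivity among those without a swab. The true rate is 0.20 × 0.92 + 0.08q = 0.184 + 0.08q.

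- q = 0: 18.4%. The SAP rule is right and the known-status figure of 20.0% is too high.
- q = 0.20: 20.0%. The known-status figure is right.

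**The case against.** The strongest reply is that few swabs should be missing. Day 7 is a scheduled clinic visit for everyone, the opt-out covers Days 2 and 3 only, and discontinued subjects get the Day 7 procedures. A visit outside its window can still yield a swab. Nothing in the documents predicts imbalance between arms or supports positivity of 20% to 30%. All of this stands, and it limits the size of the problem. It does not bring the rule into line with its reason.

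Second, the protocol wording sets no results-only denominator and is compatible with dividing by all confirmed subjects. That also stands. The protocol is silent on uncollected swabs, so the case rests on the SAP's own justification.

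Third, using culture where TCID50 is absent makes Day 7 a composite, while Days 2 and 3 remain TCID50 only. This is a real cost. However, the rule already infers a negative TCID50 from a negative culture, Protocol 8.4.1 defines the measure by culture, and the fallback avoids scoring an untitrated culture-positive sample as negative.

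Fourth, keeping missing-as-negative as the only sensitivity analysis bounds the result from below but not from above. That is fair, and is met by an optional extra row.

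**Conclusion.** The concern holds. As written, the Day 7 rule classifies subjects of unknown status as virus-negative, and its stated reason does not cover them. The reading of the text is secure; the size is not, because both p and m are assumed. Under those assumptions inflation above 5% appears only when positivity is well above 10% and missingness is clearly unequal. With equal missingness the proportions are understated but no false difference arises. If everyone without a swab is in fact virus-free, the current rule gives the right answer.

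Severity is minor. The effect is confined to the Day 7 row of display 14.2.11. The endpoint is exploratory and outside the testing hierarchy in SAP 10.4, so the primary and key secondary conclusions are untouched.

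**What to change.** In SAP 10.5.6, define Day 7 status in this order:

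1. If a TCID50 result exists, use it.
2. Otherwise, use the recorded Day 7 influenza culture result.
3. Otherwise, treat the subject as missing.

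Use subjects with known Day 7 status as the denominator and report the number missing by arm. Keep the present missing-as-negative rule as a sensitivity analysis, because the known-status denominator assumes that swabs are missing independently of virus status. A missing-as-positive row would supply the upper bound.

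The cost is one derivation rule and one or two table rows. Day 7 culture is already planned (Protocol 5.11) and listed (SAP 10.7, Table 5). The drawbacks are a slightly smaller denominator, culture standing in for TCID50 in some subjects, and the missing-data assumption just named.

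Separately, reconcile which follow-up samples are titrated. Protocol 3 and SAP 7.2 exclude samples from subjects who were influenza-negative at baseline; Protocol 5.11(2)(c)–(d) titrates when the Day 2 or Day 3 sample is positive, and titrates all positive Day 7 samples; SAP 10.5.6 makes Day 7 titration depend on culture alone. Under the SAP 7.2 wording, a subject confirmed only at Day 2 or 3 would have no Day 7 titre and would be scored negative even with a positive Day 7 culture.
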